# Endpoint to address the secondary objective

# Variables required to address the secondary objective

Secondary objective 1: To describe the safety profile of rapidly infused CT-P10 in patients with NHL or CLL in the 6 months post-index date

- Proportion of patients who experience the following safety events in the 6 months post-index date, and frequency of each per patient per month:
  - Any IRR.
  - Any grade 3 or grade 4 IRR (according to the Common Terminology Criteria for Adverse Events [CTCAE] version 4).
  - Any other AE (excluding IRR).
  - Any other grade 3 or grade 4 AE (excluding IRR).
  - o Any serious adverse event (SAE).
- Proportion of patients with AEs as the primary cause for treatment discontinuation.
- Summary distributions of event type by grade.
- Proportion of all rapid CT-P10 infusions during which IRRs were experienced.

For all AEs (temporally associated with CT-P10 treatment) during the 6 months post-index (including the index date):

- Description of AE
- IRR (Yes/No)
- Event start date
- Event end date
- Seriousness
- CTCAE v4.0 grade
- Clinician's assessment of relationship to CT-P10
- AE resulted in treatment discontinuation (Yes/No).

Secondary objective 2: To describe the clinical effectiveness of rapidly infused CT-P10 in patients with NHL or CLL in the 6 months post-index

- OS, defined as the time from the index date until death from any cause.
- Proportion of patients surviving at six months following NHL or CLL diagnosis and following the index date.
- PFS, defined as the time from the index date until the first documented evidence of disease progression or death from any cause.
- Proportion of patients surviving and free from disease progression at six months following the index date.
- Summary of best response to CT-P10

- Date of data collection.
- Patient alive at 6 months post-index (Yes / No / Not known)?
- If no, date of death (DD/MM/YYYY).
- All treatment response assessments in the post-index period (date, recorded treatment response [complete response / partial response / no response or stable disease / progressive disease], assessment based on IWCLL / Revised Response Criteria for Malignant Lymphoma / local criteria / other criteria, type(s) of

- (complete response / partial response / no response or stable disease / progressive disease).
- Proportion of patients achieving a complete or partial response.
- Time to complete or partial response, defined as the number of days from the index date until first documentation of complete or partial response by the local investigator.
- assessments used to evaluate response).
- Date (within 6 months post-index) of last recorded hospital visit.

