## 2.2 Key definitions

- **Index event:** first rapid infusion of CT-P10 (note: first rapid infusion must have been given as part of the second or a subsequent treatment cycle).
- **Index date:** date of first rapid infusion of CT-P10 (note: first rapid infusion must have been given as part of the second or a subsequent treatment cycle) (day 1).
- **Rapid infusion:** defined as a total infusion time for CT-P10 of 90 minutes or less.
- **Infusion-related reaction (IRR):** any adverse event (AE) from a pre-defined list (see Annex 3) occurring on day 1 or day 2 after an infusion of CT-P10.
- Pre-index observation period: the pre-index observation period for this study
  will be from the date of diagnosis of NHL or CLL until the index date, and will be
  used to capture patients' demographic and clinical characteristics.
- Post-index observation period: patients will be observed for a period of 6
  months after the index date (or until death, if sooner), to capture safety and
  clinical outcomes.
- Adverse event (AE): An AE is any untoward medical occurrence in a patient administered a pharmaceutical product and which does not necessarily have to have a causal relationship with this treatment. An AE can therefore be any unfavourable and unintended sign (including an abnormal laboratory finding, for example), symptom, or disease temporally associated with the use of a medicinal product, whether or not considered related to the medicinal product. The definition of an AE includes worsening of a pre-existing medical condition.

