#### 9.3 Variables

The exposure of interest in the present study is treatment with CT-P10, administered by rapid infusion as part of the second or a subsequent treatment cycle. All study patients will be exposed by definition, as this is specified in the inclusion criteria.

The endpoints associated with each of the study objectives are described below, along with the variables that will be collected in order to address the objectives. Response options for each variable will be further detailed in the electronic data collection form (eDCF).

The endpoints below will be reported using descriptive statistics of distribution, central tendency and dispersion, as appropriate for the data collected.

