# Endpoint to address the primary objective

# Variables required to address the primary objective

Primary objective: To describe the incidence of IRR associated with rapid infusion of CT-P10 in patients with NHL or CLL on day 1 or day 2 after the index event (index event defined as the first rapid infusion of CT-P10, which must have been given as part of the second or a subsequent treatment cycle).

Proportion of patients who experience an IRR\* on day 1 or day 2 after the index event.

- Did IRR(s) occur on day 1 or day 2 after the index event (Yes/No)?
- \* An IRR is defined as any AE from a predefined list (see Annex 3) occurring on day 1 or day 2 after an infusion of CT-P10.
- If yes, IRR description and date

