# Secondary objective 3: To describe treatment patterns in patients with NHL or CLL who receive treatment with rapidly infused CT-P10.

- Summary measures of the following CT-P10 treatment parameters:
  - Number of infusions
  - o Duration of infusions
  - Starting and subsequent doses
  - Chemotherapy regimen given with CT-P10 (if applicable) and premedications received
  - o Time on treatment
  - Reason why treatment was discontinued (if applicable)
- Distribution of subsequent treatment regimens (after discontinuation of CT-P10).

- For CT-P10 treatment (in the post-index period):
  - o Date of each infusion.
  - Pre-medications given.
  - Treatment doses given (actual and per m²).
  - o Duration of each infusion.
  - Name of chemotherapy regimen given with CT-P10.
  - Treatment discontinuation date (the date of discontinuation will be defined as the date of the last dose / infusion) or ongoing.
  - Treatment ongoing at 6 months post-index (Yes / No / not known).
  - Reason for permanent discontinuation (adverse event, death, disease progression, completed course of treatment, budget constraints, other).
- Name, type and start date of subsequent treatment regimens (after discontinuation of CT-P10).

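### The 6-month IRR and grade 3 or 4 IRR endpoints count reactions after any post-index CT-P10 infusion, so they do not isolate rapid infusion

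*Protocol*

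**What the plan says.** Section 9.3 of the protocol states the exposure, in terms of treatment cycles: "The exposure of interest in the present study is treatment with CT-P10, administered by rapid infusion as part of the second or a subsequent treatment". The same section words secondary objective 1 as "To describe the safety profile of rapidly infused CT-P10 in patients with NHL or CLL in the 6 months post-index date". Section 2.2 defines a rapid infusion by achieved time: "defined as a total infusion time for CT-P10 of 90 minutes or less".

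The IRR definition in section 2.2 carries no such limit. It is "any adverse event (AE) from a pre-defined list (see Annex 3) occurring on day 1 or day 2 after an infusion of CT-P10", and section 9.3 repeats it under the primary endpoint.

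The patient-level safety endpoints are given as "Proportion of patients who experience the following safety events in the 6 months post-index date, and frequency of each per patient per month". Any IRR and any grade 3 or 4 IRR are in that list, with no condition on infusion time. The list closes with one rapid-restricted measure, the proportion of rapid infusions with an IRR, which is not broken down by grade.

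For secondary objective 3 the protocol collects the date of every post-index infusion and "Duration of each infusion". For adverse events it collects start date, grade and an IRR flag.

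**The concern.** The stated exposure and the counted events do not match. An IRR qualifies if it is "occurring on day 1 or day 2 after an infusion of CT-P10", so a reaction after a later infusion lasting more than 90 minutes enters the 6-month figures alongside reactions to rapid infusions. Eligibility (section 9.2.1) needs a rapid infusion in the second or a later cycle. It does not require the infusions after it to be rapid.

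The protocol allows for mixed durations: it records the length of each infusion and restricts one endpoint to rapid ones, which would be redundant if all were rapid. Nor need the mix be random. Section 7 describes rapid infusion as used in patients without serious complications at earlier infusions, so infusion speed can depend on reaction history.

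At stake is how the 6-month figures will be read. A reader of the report would take them as the IRR and severe-IRR burden of rapid infusion. For severe reactions there is no rapid-only line to check against.

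**Working it through.** **No planned figure to reproduce.** The protocol gives no expected rate or precision for the 6-month IRR endpoints. The precision table in section 9.5 concerns IRR proportions at given sample sizes and does not bear on this point.

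**Which measures move, by patient course after index**

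| Course | Any-IRR proportion | Monthly IRR frequency | Grade 3 or 4 proportion |
|---|---|---|---|
| All later infusions stay rapid | same either way | same | same |
| IRR on a rapid infusion, then slowed, then IRR on a longer infusion | same: patient already counted | higher when all infusions count | differs only if the rapid-infusion IRR was grade 1 or 2 and the later one grade 3 or 4 |
| No IRR on a rapid infusion, IRR on a longer one | differs | differs | differs if grade 3 or 4 |
| Later infusion meant to be rapid, prolonged past 90 minutes by an IRR | rapid-only count loses it, unless the patient had another rapid-infusion IRR | rapid-only count loses it | rapid-only count loses it if grade 3 or 4, with the same exception |

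The second row matters because slowing after a reaction is the most natural reason for a change of speed. In that case the any-IRR proportion does not change.

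**Illustration of size.** Inputs:
- r_R, IRR risk per rapid infusion: 8.84%, the pooled figure in section 9.5, used here as a per-infusion risk by assumption.
- r_S, IRR risk per longer infusion: not in the protocol; assumed 2%, 8.84% and 15%.
- m, infusions from index onward: not in the protocol; assumed 4 or 6.
- s, share of infusions after the index one that run longer than 90 minutes: not in the protocol; assumed 0 to 50%.

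The index infusion is rapid by definition, so n_S = s(m − 1) and n_R = m − n_S. With infusions treated as independent:
- all infusions: 1 − (1 − r_R)^n_R × (1 − r_S)^n_S
- rapid only: 1 − (1 − r_R)^n_R
- share of IRR events from longer infusions: n_S r_S / (n_S r_S + n_R r_R)

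Worked case, m = 6, s = 25%, r_S = 8.84%: n_S = 0.25 × 5 = 1.25 and n_R = 4.75. Rapid only is 1 − 0.9116^4.75 = 35.6%. All infusions is 1 − 0.9116^6 = 42.6%. The event share is 1.25/6 = 20.8%.

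Ranges below run from r_S = 2% to 15%; differences use unrounded values.

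| m | s | All infusions | Rapid only | Difference (points) | Events from longer infusions |
|---|---|---|---|---|---|
| 6 | 0% | 42.6% | 42.6% | 0 | 0% |
| 6 | 10% | 40.5–44.6% | 39.9% | 0.6–4.7 | 2.0–13.4% |
| 6 | 25% | 37.2–47.4% | 35.6% | 1.6–11.8 | 5.6–30.9% |
| 6 | 50% | 31.2–51.8% | 27.7% | 3.6–24.1 | 13.9–54.8% |
| 4 | 10% | 29.4–32.4% | 29.0% | 0.4–3.4 | 1.8–12.1% |
| 4 | 25% | 27.1–34.5% | 26.0% | 1.1–8.5 | 5.0–28.1% |

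Two cautions apply. Independence does not describe slowing after a reaction; if that were the only reason for longer infusions, the any-IRR difference would be zero. Also, the rapid-only proportion falls partly because there are fewer rapid infusions to react to, so the difference is not all error.

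**The case against.** The strongest defence is that the endpoints suit the objective as section 8.4 words it: the 6-month safety profile in patients who receive rapid infusion. That describes a cohort followed from its first rapid infusion, and the other adverse events in the same list are not tied to infusion speed either. Where the authors wanted a speed restriction, they wrote one. This stands, and it is why the all-infusion figures should stay. It does not settle the matter, because section 9.3 words the same objective around rapidly infused CT-P10 and leaves severe IRRs without a rapid-only measure.

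A second defence is that restricting the endpoint could do harm. Section 9.9 admits that defining rapid by achieved time may exclude infusions planned for 90 minutes but delayed or stopped because of an IRR. A rapid-only endpoint would extend that under-count to every later infusion, and intended rate is not a listed variable with which to repair it. This also stands, and it rules out replacing one figure with the other.

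Third, centres are chosen for their practice of rapid infusion (section 9.2.4), so longer infusions may be few, and the analysis plan could add a split. Both are fair. The mismatch, however, lies in definitions that the protocol itself sets.

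**Conclusion.** The point holds in limited form. The 6-month any-IRR and grade 3 or 4 IRR proportions and monthly frequencies mix rapid infusions with any longer post-index ones, and so do not isolate the named exposure. The size is unknown. In the illustration the any-IRR difference runs from 0 to about 24 points, but the upper end needs six infusions, half of the later ones longer than 90 minutes, and a 15% risk on those; none of these inputs comes from the protocol.

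Three stronger readings are tempting and not supported:
- That these endpoints fail to measure rapid infusion at all. The index infusion is rapid by definition, and it and every later rapid infusion count.
- That patients slowed after a reaction inflate the any-IRR proportion. If the reaction followed a post-index rapid infusion, they are already counted. The likely effect is on the monthly frequency and possibly the grade 3 or 4 proportion.
- That a particular share of events is misattributed. The protocol gives no share of longer infusions, and it may be zero.

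The endpoints are secondary and descriptive. The primary endpoint is tied to the first rapid infusion and is untouched.

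**What to change.** In section 9.3 and the analysis plan:
1. Keep the all-infusion any-IRR and grade 3 or 4 IRR figures, labelled as describing the cohort that started rapid infusion.
2. Link each post-index IRR to the infusion on the same day or the day before, using the adverse-event start dates and the infusion dates and durations already collected.
3. Report any IRR and grade 3 or 4 IRR separately for infusions of 90 minutes or less and for longer ones, with the number of patients and infusions behind each row.
4. Add a grade 3 or 4 line to the per-rapid-infusion endpoint.
5. Do not replace the all-infusion figure with the rapid-only one. State beside the split that an infusion prolonged past 90 minutes by an IRR falls in the longer row, as section 9.9 implies.

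The cost is one derived variable, some extra table rows and fewer events per row. No new data field is needed.

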#### • **Serious adverse event (SAE):** a SAE is an AE that:

- is fatal
- o is life threatening (places the subject at immediate risk of death)
- o requires in-patient hospitalisation or prolongation of existing hospitalisation
- results in persistent or significant disability/incapacity
- o is a congenital anomaly/birth defect
- other significant medical hazard.

- **Adverse event grade:** AEs will be defined as grade 1, 2, 3, 4 or 5 according to the Common Terminology Criteria for Adverse Events v4.0 (CTCAE).
- **Overall survival (OS):** defined as the time from the index date to death from any cause.
- **Progression free survival (PFS):** defined as the time from the index date to the first documented evidence of disease progression or death from any cause. The assessment of disease progression will be based on the International Workshop on Chronic Lymphocytic Leukemia (IWCLL) criteria for CLL or the Revised Response Criteria for Malignant Lymphoma for NHL, if these criteria are used and documented locally. If different criteria are used in routine practice, disease progression will be defined as documented in the medical records.
- Complete response (CR) or partial response (PR): will be based on IWCLL criteria for CLL or the Revised Response Criteria for Malignant Lymphoma for NHL, if these criteria are used and documented locally. If different criteria are used in routine practice, response will be defined as documented in the medical records.

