# 8.4 Secondary research objectives

To describe the following in patients who receive rapid infusion of CT-P10 for the treatment of NHL or CLL:

1. Safety profile in the 6 months post-index date (index date defined as the date of the first rapid infusion of CT-P10, which must have been given as part PASS PT Celltrion RAPID v2 0 FINAL 18APR2018

Page 19 of 43

of the second or a subsequent treatment cycle), including incidence (and frequency per patient per month, where appropriate) of the following safety events: IRRs, grade 3 or grade 4 IRRs, any adverse event (AE), any serious adverse event (SAE), any grade 3 or grade 4 AE, AEs as the primary cause for treatment discontinuation.

- 2. Clinical effectiveness in the 6 months post-index date (to be analysed separately for NHL and CLL), including overall survival (OS), progression free survival (PFS), best response, overall (complete/partial) response rate, time to complete or partial response.
- 3. NHL / CLL treatment patterns during the observation period (from diagnosis of NHL or CLL to 6 months post-index date), including types and doses of treatment, number and duration of infusions, time on treatment and reasons for discontinuation.
- 4. Patients' demographic, clinical, and NHL/CLL disease characteristics.

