## 9.5 Study size

The proposed sample size for this study is 300. Given that the study is primarily descriptive, aiming to characterise the IRR rate in patients receiving rapid infusion of CT-P10, assessments of the utility of this sample size is primarily based on the precision with which rates can be estimated. The mean frequency/incidence of IRRs for rapidly infused rituximab across a range of studies was reported to be 8.84% (95% confidence interval [CI]: 7.12 to 10.81) in a meta-analysis by Polwart. Given this, 95% CIs around estimates of possible IRRs for rapidly infused CT-P10 at different sample sizes are given below:

IRR %	200 patients		250 patients		300 patients		350 patients		400 patients	
	95% LCI	95% UCI								
8%	4.6%	12.7%	5.0%	12.1%	5.2%	11.7%	5.4%	11.4%	5.5%	11.1%
9%	5.4%	13.9%	5.8%	13.3%	6.0%	12.8%	6.2%	12.5%	6.4%	12.2%
10%	6.2%	15.0%	6.6%	14.4%	6.8%	14.0%	7.1%	13.6%	7.2%	13.4%
12.5%	8.3%	17.9%	8.7%	17.2%	9.0%	16.8%	9.2%	16.4%	9.4%	16.1%
15%	10.4%	20.1%	10.8%	20.0%	11.2%	19.6%	11.4%	19.2%	11.6%	18.9%
20%	14.7%	26.2%	15.2%	25.5%	15.6%	25.0%	15.9%	24.6%	16.2%	24.3%
30%	23.7%	36.9%	24.4%	36.1%	24.9%	35.5%	25.2%	35.1%	25.5%	34.8%

Assuming the rate of IRRs in patients receiving rapid infusion of CT-P10 are similar to those found in previous rituximab studies (rounding to 10%), we can expect the 95% CIs to be between 6.8 and 14.0% with a sample size of 300; a 95% CI width of 7.2%. If the sample size for the study was increased by 100 patients, the gain in precision would be a 95% confidence interval width of 6.2%, while for 200 patients the width would increase to 8.8%. The highest IRR rates among the studies investigated by Polwart gave an IRR rate of approximately 30%. For this IRR rate the 95% confidence interval would span between 24.9 and 35.5% for a sample of 300. Given the diminishing returns of the effect of increasing study sample size on the precision of estimates derived, a sample of 300 patients is considered acceptable.

The expected sample size split for patients with NHL and CLL is based on the epidemiology of both diseases, with approximately 76,800^17 and 20,200^18 patients

with NHL and CLL, respectively, being alive at the end of 2010 in the UK. Based on these prevalence estimates, and assuming a similar prevalence across Europe, it is expected that the sample will comprise approximately 240 patients with NHL and 60 with CLL.

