quantitative variables. Categorical variables will be described with frequencies and percentages; distributions, modes, medians, IQR and range will be reported as appropriate. 95% CI will be presented for means and estimates of proportions, as appropriate. Where appropriate differences between disease groups will be evaluated using two-sample t-tests or Mann-Whitney U-tests for continuous normally and non-normally distributed variables, respectively, while the chi-squared test will be employed for nominal variables. Normality of variables will be evaluated through inspecting histograms of their distributions.

Treatment patterns for NHL or CLL in patients who receive rapid infusion of CT-P10 will be described for the entire study period. Summary statistics will be displayed for the treatment dose and duration on treatment, and for the treatment discontinuation reason.

All percentages will be reported to the nearest whole number; therefore, in reporting study results in tables, figures and associated text, percentages may not add up to 100% due to rounding.

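### The section 9.3 safety endpoints omit the any-AE totals promised in secondary objective 1, and both high-grade rows stop at grade 4

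*Protocol*

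**What the plan says.** Section 8.4 lists the safety events to be described over the six months after the index date. Besides IRRs and grade 3 or 4 IRRs, the list includes "any adverse event (AE), any serious adverse event (SAE), any grade 3 or grade 4 AE". Nothing there removes IRRs from the AE categories. The synopsis and the abstract repeat the same objective.

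Section 9.3 lists the endpoints meant to address that objective. IRRs have two rows of their own, any IRR and "Any grade 3 or grade 4 IRR". The two AE rows that follow are restricted to events other than IRRs, the high-grade one being "Any other grade 3 or grade 4 AE (excluding IRR". The same list has a row for any SAE, with no grade limit and no IRR exclusion, and a tabulation of event types by grade.

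On the grading scale, section 2.2 states that "AEs will be defined as grade 1, 2, 3, 4 or 5" under CTCAE version 4.0. Both high-grade rows in 9.3, and the wording in 8.4, name grades 3 and 4 only.

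On presentation, section 9.7.2 says: "All percentages will be reported to the nearest whole number". On size, section 9.5 says: "The proposed sample size for this study is 300".

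**The concern.** The objective and its endpoints name different quantities. Whoever writes the analysis tables from this protocol cannot tell whether AE incidence should include IRRs. If 9.3 is followed as written, the two overall figures that 8.4 promises are never produced.

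The excluded set is broad. Annex 3 counts common events such as nausea, headache, fatigue and diarrhoea as IRRs when they fall on day 1 or 2 after an infusion. The rows are also uneven: the SAE row includes IRRs while the AE rows do not, so the SAE row is not a subset of the AE row above it.

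The grade limit is a separate gap. Annex 3 includes anaphylaxis, myocardial infarction and cardiac failure. A fatal event of that kind on day 1 is an IRR by definition. It is too high a grade for the grade 3 or 4 IRR row, and as an IRR it is shut out of the other high-grade row. A fatal non-IRR event likewise falls outside the high-grade AE row. A reader of a post-authorisation safety study would normally want the share of patients with an event of grade 3 or above, and no listed row gives it.

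**Working it through.** **Inputs.** From the protocol: n = 300, with about 240 NHL and 60 CLL patients expected (9.5); the row definitions (9.3); grades 1 to 5 (2.2); whole-percent rounding (9.7.2). The protocol gives no rate for other AEs, fatal AEs or six-month IRRs, so the rates in step 2 are assumptions, shown as a range.

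**1. The plan's own figure.** Section 9.5 says "we can expect the 95% CIs to be between 6.8 and 14.0% with a sample size of 300", at a 10% IRR rate. The exact (Clopper-Pearson) interval for 30/300 takes the 2.5% quantile of Beta(30, 271) and the 97.5% quantile of Beta(31, 270). This gives 6.8% to 14.0%, so the figure reproduces. It is quoted to one decimal, finer than the reporting rule in 9.7.2. The plan gives no precision figure for the secondary safety endpoints.

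**2. Can any AE be recovered from the listed rows?** Let a be the proportion with an IRR and b the proportion with another AE. The proportion with either is bounded by

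max(a, b) ≤ any AE ≤ min(1, a + b).

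| a (assumed) | b (assumed) | any AE, bounds | if independent: 1 − (1 − a)(1 − b) |
|---|---|---|---|
| 10% | 30% | 30% to 40% | 37% |
| 10% | 50% | 50% to 60% | 55% |
| 10% | 70% | 70% to 80% | 73% |

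The 10% is the plan's rounded planning rate for the index infusion. In each row the total is uncertain by 10 points, or 0.10 × 300 = 30 patients. With a = 30%, the highest rate cited in 9.5, and b = 50%, the bounds widen to 50% to 80%. The same argument applies to any grade 3 or 4 AE, which is the union of the two high-grade rows. The totals need a patient-level count.

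**3. Effect of stopping at grade 4.** Let g be the number of patients whose only grade 3-or-higher event is grade 5. A grade 3-or-higher proportion exceeds a grade 3-or-4 proportion by g/300:

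- g = 1: 1/300 = 0.33 points
- g = 3: 3/300 = 1.0 point
- g = 9: 9/300 = 3.0 points

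The protocol gives no basis for choosing g. If no such patient exists, the difference is zero.

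**4. Rounding to whole percent.**

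- 1/300 = 0.33% prints as 0% (exact 95% CI 0.01% to 1.84%).
- 1/240 = 0.42% prints as 0%.
- 2/300 = 0.67% prints as 1%.
- 1/60 = 1.67% prints as 2%.

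Of the counts 0 to 300 out of 300, 100 round up, 100 round down and the rest are exact. Only a single patient among 300 or 240 can print as 0%.

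**The case against.** The strongest reply is that nothing is hidden. IRRs have their own rows at the top of the same list, and the AE rows are openly labelled as excluding them, so nobody would print the restricted figure as any AE. Each AE is recorded with an IRR flag, grade and seriousness, and section 11.2.1 says all AEs will be summarised in the report. The objective and endpoints agree on grades 3 and 4, and the protocol nowhere calls that category severe. A fatal AE is an SAE by definition and so enters the SAE row. It also appears in the by-grade tabulation, and deaths enter overall survival.

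Most of this stands, and it rules out a stronger reading that a reader might infer: that the grade limit, the IRR exclusion and the rounding together understate the rarest and worst events. The documents do not support that. Fatal events and IRRs are each reported elsewhere in the same endpoint list. Rounding runs equally in both directions. Counts accompany percentages for the primary endpoint (9.7.1) and for categorical variables (9.7.2), so a single event would be visible as a count even beside 0%.

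The reply does not remove the mismatch between 8.4 and 9.3, and the promised totals remain unlisted. Nor does it supply a grade 3-or-higher proportion. Seriousness is a different attribute from grade, overall survival counts death from any cause, and a distribution of events by grade is not stated to be a proportion of patients.

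**Conclusion.** The point holds as a mismatch to reconcile and a small definitional gap. It is not evidence that the safety results would be biased as a whole.

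- **Any-AE totals.** This is the firmest part and rests on the text alone. Sections 8.4 and 9.3 differ, and the totals in 8.4 cannot be derived from the rows in 9.3. The 10-point ambiguity depends on the assumed 10% IRR rate.
- **Grade 5.** The grade 3 or 4 rows fall short of grade 3-or-higher incidence by 0.33 points for each patient whose only such event is fatal. How many there would be is unknown and could be none.
- **Rounding.** This is a presentational matter only. It is not a source of systematic understatement.

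**What to change.** 1. In 8.4, and where the synopsis and abstract repeat it, and in 9.3, replace the grade 3 or 4 categories with grade 3 or higher, for IRRs and for other AEs. Show grade 5 separately as well.
2. In 9.3, add the proportion of patients with any AE and with any grade 3-or-higher AE, both including IRRs, beside the existing versions that exclude them. Objective and endpoints then agree.
3. As a minor step, report safety percentages with n/N and one decimal, so that one event in 300 reads 1/300 (0.3%).

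No new data are needed, since the IRR flag and grade are already collected for each AE. The cost is wording changes and a few more table rows. The overall AE proportions, and any high-grade proportion that gains a grade 5 event, will be slightly higher than those now listed.
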